10.7 Efficacy Subgroup Analysis

Subgroup analyses will be performed for the primary efficacy endpoint of SVR₁₂.

Within each subgroup, the percentage of subjects with SVR₁₂ within each arm and the difference between treatment arms in the percentage of subjects with SVR₁₂ will be calculated, as will the corresponding two-sided 95% Wilson score intervals. A test of homogeneity will be conducted (Zelen's exact test) to evaluate whether differences between treatment arms are consistent across subgroups (i.e., confidence intervals for the difference in SVR₁₂ rates will not be compared to the non-inferiority margin).

Tests will be conducted at the nominal 0.05 level. The 2-sided 95% Wilson score confidence interval will be produced if there are at least 10 subjects in the subgroup.

The following subgroups will be analyzed:

- HCV genotype 2 subtype (final subtype as defined in Section 10.9);
- Prior HCV treatment history (naïve or IFN-experienced);
- IL28B genotype (CC or non-CC);
- Sex (male or female);
- Age (< 65 years, ≥ 65 – < 75 years, ≥ 75 years);
- BMI (< 25, or ≥ 25 kg/m²);
- Baseline HCV RNA level (< 100,000 IU/mL or ≥ 100,000 IU/mL;
< 800,000 IU/mL or ≥ 800,000 IU/mL; < 6,000,000 or ≥ 6,000,000 IU/mL;
< 10,000,000 IU/mL, or ≥ 10,000,000 IU/mL);
- Baseline fibrosis stage (F0 – F1, F2, F3, F4 (if applicable));
- Baseline platelet count (< 100 or ≥ 100 × 10⁹/L; < 150 or ≥ 150 × 10⁹/L);
- Baseline HOMA-IR (< 2 or ≥ 2 mU × mmol/L²) and (< 3 or
≥ 3 mU × mmol/L²);
- Baseline albumin (< 35 or ≥ 35 g/L);
- Baseline creatinine clearance (< 60, ≥ 60 to < 90, ≥ 90 mL/min);
- Baseline eGFR (< 30, ≥ 30 to < 60, ≥ 60 to < 90, ≥ 90 mL/min/1.73 m²);
- History of diabetes (yes/no);
- History of bleeding disorders (yes/no);
- History of depression or bipolar disorder (yes/no);
- History of cardiovascular disease (yes/no);
- Baseline metabolic syndrome (yes/no);
- Injection drug use (yes, within last 12 months; yes, more than 12 months ago;
or no);
- Presence of baseline resistance-associated variants (any NS3 variant [yes/no];
any NS5A variant [yes/no]; any NS3 and any NS5A [yes/no], any NS3 or any
NS5A [yes/no]) and (NS3 only, NS5A only, both NS3 and NS5A, or none);

- Concomitant use of Proton Pump Inhibitors (PPIs) (yes/no);
- DAA compliance (yes/no);
- Concomitant treatment with liver protectants (yes/no);
- Subject with high risk of carcinogenesis (Yes/No);
- Subject with advanced fibrosis (Yes/No).

Subgroup analysis will also be performed on relevant combinations of subgroup variables if deemed clinically meaningful.

For the subgroup analyses, the presence of baseline resistance-associated variants as listed above are defined in Section 10.9.1.

All subgroup analyses will be performed for SVR₄ in the interim analysis except

- Presence of baseline resistance-associated variants (any NS3 variant [yes/no]; any NS5A variant [yes/no]; any NS3 and any NS5A [yes/no], any NS3 or any NS5A [yes/no]) and (NS3 only, NS5A only, both NS3 and NS5A, or none).

A logistic regression model will be used to explore the associations between each of the subgroup variables and SVR₁₂ by fitting a logistic regression model on all subjects in the mITT-GT-VF population. Among all candidate predictors, continuous measurements will be used where possible (e.g., continuous baseline log₁₀ HCV RNA level) in the logistic regression model. For the variables on presence of baseline resistance-associated variants, only one unique variable (NS3 only vs. NS5A only vs. both NS3 and NS5A vs. none) will be used in the logistic regression model. A stepwise logistic regression approach will be used to assess the strength of each subgroup variable in predicting SVR₁₂, with a significance level of 0.10 to enter and remain in the model.

10.8 Additional Efficacy Analyses

The following additional efficacy endpoints will be summarized and analyzed for each treatment arm:

- The percentage of subjects with HCV RNA < LLOQ at each post-baseline visit in the Treatment Period (using data as observed);
- The percentage of subjects with SVR₂₄;
- The percentage of subjects with SVR₄ in Arm B;
- The reasons for not achieving SVR₁₂ and the reasons for not achieving SVR₂₄
- The percentage of subjects with virologic failure through Post-Treatment Week 4 (i.e., the SVR₄ non-responders due to on-treatment virologic failure or Relapse₄).
- The percentage of subjects with virologic failure through Post-Treatment Week 12 (i.e., the SVR₁₂ non-responders due to on-treatment virologic failure or Relapse₁₂).

In the above analyses for SVR and relapse, the percentage of subjects in each treatment arm with a two-sided 95% Wilson score interval and the (unadjusted) difference in rates (Arm A minus Arm B) with a two-sided 95% Wilson score interval will be summarized. Imputations for missing data will be performed as described in Section 6.3 for analyses of SVR and virologic failure, where a missing response will be imputed as a failure after performing the described imputation. All other endpoints will be presented using data as observed.

A summary of the subjects who completed treatment and relapsed (defined as **Relapse_{overall}**) will be prepared displaying the number of subjects relapsing overall and by SVR visit window (within the SVR₄, SVR₁₂, SVR₂₄ windows or after SVR₂₄ window), including the subject numbers and the SVR visit window corresponding to the first occurrence of relapse. A similar summary and listing will be prepared for subjects who prematurely discontinued treatment and relapsed after having HCV RNA < LLOQ at their Final Treatment Visit.

The number and percentage of subjects who do not achieve SVR₁₂ will be summarized by reason for non-response (as defined in Section 10.1). A listing of subject numbers and reason for non-response will be prepared. A similar summary and listing will be prepared for subjects who do not achieve SVR₄ and SVR₂₄.

The concordance between SVR₁₂ and SVR₂₄ will be assessed for each treatment arm by the agreement between SVR₁₂ and SVR₂₄ and the positive predictive value (PPV) and negative predictive value (NPV) of SVR₁₂ on SVR₂₄. The agreement between SVR₁₂ and SVR₂₄ is a percentage defined as the number of subjects achieving both SVR₁₂ and SVR₂₄ and the number of subjects where both SVR₁₂ and SVR₂₄ are not achieved. The PPV of SVR₁₂ on SVR₂₄ is the proportion of subjects who achieve SVR₂₄ out of all subjects who achieved SVR₁₂. The NPV of SVR₁₂ on SVR₂₄ is the proportion of subjects who do not achieve SVR₁₂ out of all subjects who did not achieve SVR₁₂. Similarly, the concordance between SVR₄ and SVR₁₂ will be summarized.

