6.3 Missing Data Imputation

Missing Data Imputation for SVR

HCV RNA values will be selected for analysis based on the analysis windows defined in Section 6.2. HCV RNA values from central laboratory will be used as described in Section 10.1, unless otherwise specified.

For analyses of SVR, subjects missing a visit HCV RNA value will have backward imputation applied, if possible. For backward imputation, if the nearest HCV RNA value after the SVR window is unquantifiable or undetectable, then it will be used to impute the HCV RNA value in the SVR window. If a subject continues to be missing an HCV RNA value within the appropriate SVR window after performing backward imputation, then this value will be imputed using an HCV RNA value from a local laboratory if available; otherwise, the HCV RNA value for that window will be considered missing. Subjects with missing HCV RNA data in the analysis window, after applying these imputations, will be imputed as a failure of viral response.

Regardless of the imputation method described above, if a subject starts another treatment for HCV, then all HCV RNA values for this subject measured on or after the start date of the new HCV treatment will be excluded from analyses. The subject will be considered a failure for summaries of viral response at all time points after the start of the new HCV treatment.

Missing Data Imputation for Virologic Failure

If HCV RNA values from the central laboratory are missing but a local laboratory value is available in the appropriate time period, then the local laboratory data will be used to assess post-treatment relapse and on-treatment virologic failure.

Missing Data Imputation for PRO Questionnaires

For EQ-5D-3L index and VAS scores, no imputation will be performed for missing items. The missing items of the FSS questionnaire will be imputed with the average score of the answered items as long as more than 50% of the items on the FSS are answered.

If a subject starts another treatment for HCV, then all PRO values for this subject measured on or after the start date of the new HCV treatment will be excluded from analyses.

No imputation will be performed for missing data in other than specified above.

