10.0 Efficacy Analysis

10.1 General Considerations

General Considerations

Treatment effects will be evaluated based on a 2-sided significance level of 0.050 (when rounded to three decimal places), and all efficacy analyses will be performed on the ITT population, unless otherwise specified.

Missing data will be imputed as described in Section 6.3 for analyses of the HCV RNA endpoints of SVR.

Plasma HCV RNA levels will be determined for each sample collected by the central laboratory using the Roche COBAS[®] AmpliPrep/COBAS[®] TaqMan[®] HCV Quantitative Test, v2.0. The lower limit of detection (LLOD) and lower limit of quantification (LLOQ) for this assay (regardless of genotype) are both 15 IU/mL.

HCV RNA results that are detectable but not quantifiable are reported as "< 15 IU/ML HCV RNA DETECTED" and those that are undetectable are reported as "HCV RNA NOT DETECTED" in the database.

The notation "HCV RNA < LLOQ" is used to represent all HCV RNA values < 15 IU/mL, including values reported as "HCV RNA NOT DETECTED" or "< 15 IU/ML HCV RNA DETECTED." HCV RNA \geq LLOQ are all quantifiable values.

IL28B rs12979860 will be resulted as C/C, C/T, or T/T by the central laboratory.

Definitions for Efficacy Endpoints

A confirmed quantifiable value during treatment is defined as any two consecutive HCV RNA measurements \geq LLOQ (or 100 IU/mL for **Breakthrough**), either both during treatment or at the final treatment measurement and the next consecutive post-treatment measurement. A confirmed quantifiable post-treatment value is defined as any two consecutive post-treatment HCV RNA measurements \geq LLOQ.

Breakthrough = confirmed HCV RNA \geq 100 IU/mL after HCV RNA $<$ LLOQ during the Treatment Period; or confirmed increase from nadir in HCV RNA (two consecutive HCV RNA measurements $>$ 1 \log_{10} IU/mL above nadir) at any time point during the Treatment Period. A single breakthrough value (\geq 100 IU/mL or $>$ 1 \log_{10} above nadir) followed by lost to follow-up also will be considered a breakthrough (i.e., will not require confirmation).

EOT failure = HCV RNA \geq LLOQ at end of treatment with at least 6 weeks of treatment, where the HCV RNA value must be collected on or after Study Drug Day 36 and study drug duration \geq 36 days.

On-treatment virologic failure = Breakthrough or EOT failure.

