SVR₄ = HCV RNA $<$ LLOQ in the SVR₄ window (4 weeks after the last actual dose of study drug) without any confirmed quantifiable (\geq LLOQ) post-treatment value before or during that SVR window.

SVR₁₂ = HCV RNA $<$ LLOQ in the SVR₁₂ window (12 weeks after the last actual dose of study drug) without any confirmed quantifiable (\geq LLOQ) post-treatment value before or during that SVR window.

SVR₂₄ = HCV RNA $<$ LLOQ in the SVR₂₄ window (24 weeks after the last actual dose of study drug) without any confirmed quantifiable (\geq LLOQ) post-treatment value before or during that SVR window.

Relapse₄ = confirmed HCV RNA \geq LLOQ between end of treatment and 4 weeks after last actual dose of study drug (up to and including the SVR₄ assessment time point) for a subject with HCV RNA $<$ LLOQ at Final Treatment Visit who completed treatment (defined as study drug duration \geq 52 days for Arm A and \geq 77 days for Arm B), excluding reinfection as described below.

Relapse₁₂ = confirmed HCV RNA \geq LLOQ between end of treatment and 12 weeks after last actual dose of study drug (up to and including the SVR₁₂ assessment time point) for a

subject with HCV RNA < LLOQ at Final Treatment Visit who completed treatment (defined as study drug duration ≥ 52 days for Arm A and ≥ 77 days for Arm B), excluding reinfection as described below.

Relapse₂₄ = confirmed HCV RNA \geq LLOQ within the SVR₂₄ window for a subject who achieved SVR₁₂ and has HCV RNA data available in the SVR₂₄ window, excluding reinfection.

Relapse_{overall} = confirmed HCV RNA \geq LLOQ between end of treatment and up to and including the last HCV RNA measurement collected in the PT Period for a subject with HCV RNA < LLOQ at Final Treatment Visit who completed treatment (defined as study drug duration ≥ 52 days for Arm A and ≥ 77 days for Arm B), excluding reinfection.

Only subjects who have at least one post-treatment HCV RNA value will be included in analyses of relapse. For the analysis of relapse, completion of treatment is defined as any subject with study drug duration of 52 days or greater for Arm A and 77 days or greater for Arm B. If the last available post-treatment value is \geq LLOQ, then the subject will be considered a relapse (i.e., will not require confirmation).

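### Concordance of SVR4, SVR12 and SVR24 counts a missing later HCV RNA value as a failed prediction, so PPV and agreement partly measure attendance; the NPV as printed is always 100%

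*SAP*

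**What the plan says.** Section 6.3 sets the order of imputation for SVR. Backward imputation comes first: "if the nearest HCV RNA value after the SVR window is unquantifiable or undetectable, then it will be used to impute" the value in the window. A local-laboratory value comes next. After that, "Subjects with missing HCV RNA data in the analysis window, after applying these imputations, will be imputed as a failure of viral response".

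Section 10.1 gives the rule its scope: "Missing data will be imputed as described in Section 6.3 for analyses of the HCV RNA endpoints of SVR". The ITT population is the default. Section 10.8 repeats the rule for SVR and virologic failure, "where a missing response will be imputed as a failure after performing the described imputation", and then adds: "All other endpoints will be presented using data as observed".

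The concordance paragraph of Section 10.8 follows. PPV is defined as: "The PPV of SVR₁₂ on SVR₂₄ is the proportion of subjects who achieve SVR₂₄ out of all subjects who achieved SVR₁₂". Agreement counts subjects who achieve both endpoints and subjects who achieve neither; no denominator is given. The NPV as printed has SVR12 non-responders in both numerator and denominator. The paragraph closes with: "Similarly, the concordance between SVR₄ and SVR₁₂ will be summarized". It does not ask for HCV RNA data in both windows.

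Section 10.1 does ask for this elsewhere. Relapse24 is defined only "for a subject who achieved SVR₁₂ and has HCV RNA data available in the SVR₂₄ window, excluding reinfection".

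**The concern.** Counting missing as failure is a conservative rule for a response rate. Concordance asks something else: if virus is absent at the earlier time point, is it still absent at the later one? A subject with no later measurement cannot answer that, yet the rule supplies an answer.

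The effect depends on when the subject is lost:

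- Lost after responding at the earlier time point, with no usable later value: counted as a failed prediction. PPV and agreement fall.
- Lost before both windows: non-responder at both, so counted as agreement without any virologic information.

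The first effect matters more. Few virologic failures are expected, so a handful of missed final visits can make up most of the apparent discordance. The two arms can then differ in PPV because attendance differs.

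**Working it through.** The SAP states no concordance figure, so there is nothing to reproduce. The check builds the SVR12 by SVR24 table twice: under the SAP rule, and among subjects with data.

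**Inputs.** Arm sizes of 80 and 40 (Section 4.2) and planning SVR12 rates of 96% and 95% (Section 4.3). These give 0.96 × 80 = 76.8, taken as 77 responders and 3 non-responders in Arm A, and 0.95 × 40 = 38 responders and 2 non-responders in Arm B. The numbers missing are assumptions, shown as a range. Missing here means no value in the SVR24 window, no later value below LLOQ and no local value. The agreement denominator is assumed to be all ITT subjects in the arm.

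**Formulas under the SAP rule.** Let R be the SVR12 responders, m those of them with no usable later value, r true late relapses, F the SVR12 non-responders and N the arm size.

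- PPV = (R − m − r) / R
- Agreement = (R − m − r + F) / N

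**Among subjects with data**, PPV = (R − m − r) / (R − m).

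**No true late relapse (r = 0).** Among subjects with data, PPV and agreement are 100% in every row.

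| Arm | m | PPV, SAP rule | Agreement, SAP rule |
|---|---|---|---|
| A | 2 | 75/77 = 97.4% | 78/80 = 97.5% |
| A | 4 | 73/77 = 94.8% | 76/80 = 95.0% |
| A | 8 | 69/77 = 89.6% | 72/80 = 90.0% |
| B | 2 | 36/38 = 94.7% | 38/40 = 95.0% |

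**One true late relapse and four missing, Arm A.** SAP rule: 72/77 = 93.5%. Among subjects with data: 72/73 = 98.6%.

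**Loss before both windows, Arm A.** Take 3 observed failures, 4 subjects lost early and 1 late relapse. SVR12 responders number 80 − 3 − 4 = 73, of whom 72 achieve SVR24. The concordant negative cell holds 3 + 4 = 7 subjects instead of 3. Agreement is (72 + 7)/80 = 98.75% under the SAP rule and (72 + 3)/76 = 98.68% among subjects with data. The cell changes a good deal; the percentage hardly moves.

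**NPV as printed.** With k SVR12 non-responders it is k/k = 100% whenever k > 0, whatever happens at SVR24. Dropout cannot alter it until the numerator is corrected. After that, a subject lost before both windows would count as a correct negative prediction.

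**Backward imputation.** A missing SVR12 value can be filled from an SVR24-window value below LLOQ. The earlier result is then taken from the later one, and the pair agrees by construction.

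**The case against.** The concordance paragraph states no missing-data rule of its own, so it could be read as falling under the data-as-observed sentence of Section 10.8. That reading is possible but weak: the table is built from SVR12 and SVR24, and those variables carry the imputation. If data as observed was intended, the same edit would make it explicit.

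Concordance of the two endpoints as the trial reports them is also a legitimate target, and Relapse24 is a different endpoint, so its data requirement does not contradict the PPV definition. This stands. The point concerns what the PPV can be taken to mean.

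The causes are visible elsewhere. Section 10.1 separates missing follow-up from relapse among the reasons for non-response, and Section 10.8 lists subjects by reason. A reader could trace each discordant subject, but the reported PPV would stay the same.

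Imputation also limits the problem. A skipped visit is not automatically a failure, because the SVR windows are wide and a later value below LLOQ or a local value fills the gap. SVR12 can be filled from Week 24, so the SVR4/SVR12 half is less exposed.

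Four stronger readings are tempting, and the SAP does not support them:

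- That dropout is labelled relapse. The paragraph never calls discordance relapse; the two merely have the same numerical effect.
- That a missed visit outweighs a relapse. Each counts as one subject.
- That agreement is materially inflated by early loss. The calculation shows a trivial change.
- That the Japanese submission rests on this table. Section 4.5 ties the SVR4 interim analysis to the submission, but not the concordance. That analysis takes place at Post-Treatment Week 4, before SVR12 is complete.

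**Conclusion.** The concern holds in a limited form. On the most natural reading of Sections 6.3, 10.1 and 10.8, an early responder without a usable later value lowers PPV and agreement as a relapse would. Without late relapse, the Arm A PPV falls by 2.6, 5.2 or 10.4 percentage points for 2, 4 or 8 such subjects; the Arm B PPV falls by 5.3 points for 2. These sizes rest on assumed numbers missing and on the planning response rates, since the SAP gives no dropout rate. Subjects lost before both windows enlarge the agreeing negative cell but barely change the agreement percentage.

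The NPV error needs no assumption: as printed it is 100% whenever it is defined.

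This is a descriptive additional analysis with no test or decision attached. The primary non-inferiority conclusion is unaffected. The change is worth making because it is cheap and makes the PPV measure prediction rather than attendance.

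**What to change.** Amend the concordance paragraph of Section 10.8 for both pairs of time points:

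- Compute agreement, PPV and NPV among subjects with a usable HCV RNA value (observed, backward-imputed or local) for both windows.
- Also keep every subject with known virologic failure (on-treatment failure or relapse) as a non-responder from that point on, even if later values are missing or excluded after new HCV treatment. A plain filter on data in both windows would drop early failures who leave or are retreated, and with 0.04 × 80 + 0.05 × 40 = 5.2 SVR12 failures expected over both arms it could nearly empty the negative cell.
- Report reinfections, and the number missing at either time point, separately by arm.
- Flag earlier values that were backward-imputed from the later window.
- State the agreement denominator.
- Correct the NPV numerator to subjects who do not achieve SVR24, among those who did not achieve SVR12.
- Keep the version that counts missing as failure as a supplement.

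The cost is a few sentences, a change to the program's analysis set, slightly smaller denominators and one extra table. No new data are needed.

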5.1.2 Modified Intent-to-Treat (mITT) Populations

Sensitivity analyses of the primary efficacy endpoint, when applicable, will be performed on two modified ITT populations below:

Modified ITT Genotype (mITT-GT) Population

mITT-GT population includes subjects in the ITT population excluding subjects with genotype other than HCV GT2 infection as determined in Section 10.9.

Modified ITT Genotype and Virologic Failure (mITT-GT-VF) Population

mITT-GT-VF includes all subjects in the ITT-GT population defined above, excluding subjects who did not achieve SVR₁₂ for reasons other than virologic failure.

Demographic analyses will also be performed on the mITT population(s), if needed.

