HCV reinfection is defined as confirmed HCV RNA \geq LLOQ after the end of treatment in a subject who had HCV RNA < LLOQ at Final Treatment Visit, along with the post-treatment detection of a different HCV genotype, subtype, or clade compared with baseline, as determined by phylogenetic analysis of the NS3 or NS5A, and/or NS5B gene sequences. Reinfection in the case of the same HCV subtype is defined as a clade switch, as indicated by the lack of clustering between the baseline and post-treatment sequences by phylogenetic analysis. If phylogenetic analysis is not possible due to technical difficulties, HCV reinfection may be determined with a confirmed HCV genotype or subgenotype switch by the Versant HCV Genotype Inno-LiPA Assay v2.0 or Sanger assay.

Post-treatment relapse is defined as described earlier (**Relapse₁₂**, **Relapse₂₄**, **Relapse_{overall}**), and no genotype, subtype, or clade switch compared with baseline as

determined by phylogenetic analysis of the NS3 or NS5A gene sequences. If phylogenetic analysis is not possible due to technical difficulties, the subject will be defined as having a post-treatment relapse unless an HCV genotype or subgenotype switch is confirmed by the Versant HCV Genotype Inno-LiPA Assay v2.0 or Sanger assay.

Reasons for SVR₄ Non-Response

Subjects who do not achieve SVR₄ (SVR₄ non-responders) will be categorized as having:

1. On-treatment virologic failure (see **On-treatment virologic failure** definition);
2. Relapse by Post-Treatment Week 4 (defined according to the **Relapse₄** definition for subjects who complete treatment);
3. Prematurely discontinued study drug with no on-treatment virologic failure (defined as any SVR₁₂ non-responder who prematurely discontinued study drug [study drug duration < 52 days for subjects in Arm A, and < 77 days for subjects in Arm B] and did not meet the **On-treatment virologic** failure definition);
4. HCV reinfection (see definition described earlier);
5. Missing follow-up data in the SVR₄ window (defined as any subject who completed study drug without data in the SVR₄ window after applying the imputation rules and not meeting the definitions of [1], [2], [3], or [4]);
6. Other (defined as any SVR₄ non-responder not meeting the definitions of [1] – [5]).

Reasons for SVR₁₂ Non-Response

Subjects who do not achieve SVR₁₂ (SVR₁₂ non-responders) will be categorized as having:

1. On-treatment virologic failure (see **On-treatment virologic failure** definition);

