10.6 Sensitivity Analyses for SVR

The following analysis approaches will be used as sensitivity analyses for evaluating SVR₁₂ rates within and between treatment arms for the primary efficacy endpoint:

- A two-sided 95% confidence interval for the SVR₁₂ rates within each arm will be calculated using a Wilson score interval.
- The percentage of subjects achieving SVR₁₂ will be compared using a logistic regression model with treatment arm as a factor, and baseline log₁₀ HCV RNA level, HCV genotype 2 subtype, and prior HCV treatment history as covariates.

- The difference in SVR₁₂ rates (Arm A minus Arm B) will be analyzed using a stratum-adjusted Mantel-Haenszel (MH) proportion with a continuity correction for variance, adjusting for both of the randomization stratum (described in Section 5.2).
- A two-sided 95% confidence interval for the difference in SVR₁₂ rates (Arm A minus Arm B) will be calculated using a Wilson score interval.

The above analyses will be performed on the ITT, and mITT-GT-VF populations, as applicable. The same sensitivity analyses will be performed for SVR₄ in the interim analysis.

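### Three SAP rules name the wrong SVR time point: the NPV of SVR12 on SVR24, category 3 of the SVR4 non-response list, and the mITT-GT-VF population at the interim

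*SAP*

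**What the plan says.** **NPV.** SAP Section 10.8 assesses how well SVR12 predicts SVR24 in each arm. The PPV is written properly: "The PPV of SVR₁₂ on SVR₂₄ is the proportion of subjects who achieve SVR₂₄ out of all subjects who achieved SVR₁₂". The next sentence defines the NPV as the "proportion of subjects who do not achieve SVR₁₂ out of all subjects who did not achieve SVR₁₂". The other pair is covered in one line: "Similarly, the concordance between SVR₄ and SVR₁₂ will be summarized".

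**SVR4 reasons.** Section 10.1 lists six categories for subjects who fail SVR4. Category 3, early discontinuation without on-treatment virologic failure, is "defined as any SVR₁₂ non-responder who prematurely discontinued study drug". Category 5 (missing data) covers "any subject who completed study drug without data in the SVR₄ window after applying the imputation rules". Category 6 is the residual class and refers to SVR4. In the SVR24 list, the matching early-discontinuation category refers to SVR24.

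**Population.** Section 5.1.2 builds mITT-GT-VF by "excluding subjects who did not achieve SVR₁₂ for reasons other than virologic failure". Section 10.6 runs the sensitivity analyses on ITT and mITT-GT-VF, as applicable, and adds: "The same sensitivity analyses will be performed for SVR₄ in the interim analysis". No SVR4 version of the population is given. Section 10.6.1 also repeats its imputation analyses for SVR4. One of them recodes early discontinuers without on-treatment failure, and subjects with missing follow-up, as successes.

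**The concern.** Each rule is an instruction to programmers, and each points at the wrong visit.

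- An NPV with the same event above and below the line carries no information, but in a report it would read as perfect prediction.
- The SVR4 reason table and the interim mITT-GT-VF depend on SVR12. The interim takes place when all subjects have completed Post-Treatment Week 4 or discontinued, so many will have no SVR12 status yet.

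At stake are the concordance summary, the SVR4 reason table, and those interim sensitivity analyses that use mITT-GT-VF or category 3. Section 4.5 says the interim will support regulatory submission activities in Japan.

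**Working it through.** The SAP states no figure on this point, so there is none to reproduce.

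**1. NPV**

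Let k be the SVR12 failures in an arm and j the number of those who achieve SVR24.

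- As written: k/k = 100% for every k ≥ 1, and 0/0 for k = 0.
- As the PPV sentence implies it should be: (k − j)/k.

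The inputs from Section 4.3 are 80 subjects at 96% in Arm A and 40 at 95% in Arm B.

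| | Arm A | Arm B |
|---|---|---|
| Expected SVR12 failures | 80 × 0.04 = 3.2 | 40 × 0.05 = 2.0 |
| Chance of no failure (NPV undefined) | 0.96^80 = 3.8% | 0.95^40 = 12.9% |
| Arithmetically possible NPV at about that k | k = 3: 100, 66.7, 33.3 or 0% | k = 2: 100, 50 or 0% |
| NPV as written | 100% | 100% |

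The lower values in the third row are possible arithmetically but unlikely under the SAP's own definitions:

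- SVR24 requires that no confirmed quantifiable post-treatment value has occurred (Section 10.1), so a confirmed relapser cannot count as j.
- A subject with no SVR12 value whose nearest later value is unquantifiable or undetectable is imputed backward as an SVR12 success (Section 6.3) and leaves k.
- A subject who starts another HCV treatment is a failure from then on (Section 6.3).

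What remains is essentially an isolated, unconfirmed quantifiable value in or just after the SVR12 window. So j is probably 0 or very small.

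**2. SVR4 category 3**

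Table 3 puts the SVR4 window at Study Drug End Days 3 to 56 and the SVR12 window at Days 57 to 126. A subject with data only through Post-Treatment Week 4 has nothing in the SVR12 window.

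Take an early discontinuer who fails SVR4, with no on-treatment virologic failure and no reinfection. Relapse by Week 4 and category 5 both require completed treatment, so only categories 3 and 6 remain.

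- If SVR12 status is treated as unknown, category 3 is not met. The subject goes to the residual class and misses the recoding as success in Section 10.6.1.
- If the Section 6.3 rule (still missing means failure) is applied to SVR12 early, category 3 is met.
- If a confirmed quantifiable post-treatment value already exists, the subject is an SVR12 non-responder on any reading, and category 3 is met.

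The wording can also matter once SVR12 is known. An early discontinuer whose last SVR4-window value is quantifiable but unconfirmed, and who then achieves SVR12, fails SVR4 but cannot enter category 3.

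**3. Interim mITT-GT-VF**

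- If missing SVR12 counts as failure, an SVR4 responder who completed treatment but has no SVR12-window data is an SVR12 non-responder for a non-virologic reason and is excluded. With r SVR4 responders, f virologic failures and m responders excluded in this way, the rate becomes (r − m)/(r − m + f). For f > 0 this is below r/(r + f) and falls as m grows.
- If unknown SVR12 does not count as failure, subjects who failed SVR4 for non-virologic reasons can stay in, which defeats the purpose of the population.

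Neither reading gives the intended set. The size of m depends on enrolment pace, which the SAP does not state.

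**The case against.** The best defence is that these are slips of a subscript with an obvious meaning. The NPV is named for SVR12 on SVR24 and follows a correct PPV. *Similarly* need not carry the slip over to the SVR4–SVR12 pair. *As applicable* in Section 10.6 leaves room for judgement. Section 4.5 rules out inference and treatment decisions at the interim. This stands as far as intent and overall impact go. It does not supply the missing definitions: the SVR4–SVR12 NPV has no correct template to follow, and *as applicable* does not create an SVR4-based population.

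Three stronger readings are tempting and are not supported:

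- **That the formula hides a poor NPV.** Sections 6.3 and 10.1 leave almost no route from SVR12 failure to SVR24 success, so the corrected figure should also be near 100%.
- **That every early discontinuer who fails SVR4 would be misfiled.** On-treatment failure goes to category 1 and reinfection to category 4, neither of which depends on SVR12. Some subjects will already have a known SVR12 status at the interim, and the missing-as-failure reading puts the rest in category 3.
- **That the interim sensitivity analyses cannot be run.** Those on the ITT population that do not use category 3 are untouched, and the others can be run once the time point is corrected.

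**Conclusion.** The point holds as a set of three wording errors in operative rules, and it should be corrected.

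- The NPV is an identity: 100% for any arm with at least one SVR12 failure, undefined otherwise. This rests on no assumption. The expected denominators of 3.2 and 2.0 rest on the SAP's planned numbers and assumed SVR12 rates.
- Misfiling under SVR4 category 3 is possible for some early discontinuers. How many depends on how unknown SVR12 status is handled and on how many subjects have reached Day 57 at the interim. The SAP fixes neither.
- The SVR12-based mITT-GT-VF cannot be applied properly at Post-Treatment Week 4. With missing counted as failure it excludes SVR4 responders.

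A reader might infer that the main efficacy conclusion is at risk. It is not: the primary analysis in Section 10.3 compares SVR12 rates in the ITT population and uses none of these three rules. The gain from correcting the NPV is that a value near 100% would then be a finding and not a consequence of the formula.

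**What to change.** 1. Section 10.8: define the NPV of SVR12 on SVR24 as subjects not achieving SVR24 out of all subjects not achieving SVR12. State the NPV of SVR4 on SVR12 explicitly as subjects not achieving SVR12 out of all subjects not achieving SVR4. State that the NPV is not calculated when an arm has no failure at the earlier time point. Show the counts beside the percentage.
2. Section 10.1, SVR4 list, category 3: refer to SVR4 non-responders.
3. Section 5.1.2 (or 10.6): for the interim, define mITT-GT-VF as mITT-GT minus subjects who did not achieve SVR4 for reasons other than virologic failure. Keep the SVR12-based definition for the primary analysis.

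Keep the existing missing-data rules. Restricting the NPV to subjects with HCV RNA data in both windows is not needed. It would be a new analysis set, would depart from Section 10.8, which counts all subjects and treats missing response as failure, and could shrink denominators that are already about 3.2 and 2.0.

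The cost is three wording changes before the interim programs are finalised. No new data are needed, and sample size and the primary analysis do not change.
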